3.2 Schedules of Assessments

Table 1 Schedule of Assessments: Cohorts 1 and 2 – Subjects NOT Receiving Booster Dose

Study Visit	V00	V01	V02	V03	V04	V05	V06	V07	V08	Unsch Visit	Early Term Visit
Study Day(s)	SCR -30 to -1	Day 1	Day 2 +1d	Day 4 +2d	Day 8 +2d	Day 29 ±3d	Day 57 ±3d	Day 180 ±3d	Day 365 ±7d		
Obtain Written Informed Consent	X										
Review Eligibility Criteria	X	X									
Medical History	X										
Review of Interim Medical History		X	X	X	X	X	X	X	X	X	X
Concomitant Medications	X	X	X	X	X	X	X	X	X	X	X
Vital Signs (Oral Temp, Pulse, BP)	X	X			X	X	X	X	X	X	X
Physical Examination Including Height and Weight	X										
Targeted Physical Examination, if Indicated		X			X	X	X	X	X	X	X
Nasal Swab Collection for SARS-CoV-2 PCR	X										X ⁷
Blood Collection for Safety Labs	X ¹				X ²		X ²	X ²		X ²	X ²
Blood Collection for HBsAg, Anti-HCV, SARS-CoV-2 Serology ³ , HIV	X						X ³				
Blood Collection for Cellular Immune Assays		X			X	X		X	X	X	X
Blood Collection for Antibody Assays		X				X	X	X	X	X	X
Vaccination		X									
45 Minute Evaluation After Study Vaccination		X									
Distribute Memory Aid and Study-Related Materials		X									
Review Memory Aid			X	X	X					X ⁴	X ⁴

Study Visit	V00	V01	V02	V03	V04	V05	V06	V07	V08	Unsch Visit	Early Term Visit
Study Day(s)	SCR -30 to -1	Day 1	Day 2 +1d	Day 4 +2d	Day 8 +2d	Day 29 ±3d	Day 57 ±3d	Day 180 ±3d	Day 365 ±7d		
Adverse Events		X	X	X	X	X				X ⁵	X ⁵
SAEs/AESIs Including PIMMCs/MAAEs/NOCMCs ⁸		X ⁹	X	X	X	X	X	X	X	X	X
Phone Visit ⁶			X	X							
Saliva Collection for Antibodies		X			X			X			

Abbreviations: AESI, adverse event of special interest; BP, blood pressure; HBsAg, hepatitis B surface antigen; HCV, hepatitis C virus; HIV, human immunodeficiency virus; MAAE, Medically Attended Adverse Event; NOCMC, New Onset Chronic Medical Condition; SAE, serious adverse event; PCR, polymerase chain reaction; PIMMC, Potentially Immune-Mediated Medical Condition; SARS-CoV-2, severe acute respiratory syndrome coronavirus 2; SCR, screening; Unsch, unscheduled

- Includes white blood cells (WBCs), hemoglobin (Hb), platelets (PLT), alanine aminotransferase (ALT), aspartate aminotransferase (AST), alkaline phosphatase (ALP), total bilirubin, creatine kinase (CK), serum creatinine, prothrombin time (PT)/international normalized ratio (INR), and activated partial thromboplastin time (aPTT)
- Includes WBCs, Hb, PLT, ALT, AST, ALP, total bilirubin, CK, and serum creatinine
- Includes SARS-CoV-2 serology (N-specific) only
- If within 7 days after vaccination
- If prior to Visit 05
- Can be phone, text, or e-mail contact
- A nasal swab for SARS-CoV-2 should be performed within 3 days of COVID-19 symptoms and repeated after 7 days.
- AESIs, including serologically or virologically confirmed SARS-CoV-2 infection and severity of COVID-19, PIMMCs, MAAEs, and NOCMCs will be collected from the time of first vaccination throughout the entire study.
- SAEs occurring after signing of the informed consent form (ICF) will be recorded and reported to the sponsor or designee by the investigator within 24 hours of becoming aware of the SAE.

Table 2 Schedule of Assessments: Cohorts 1 and 2 – Subjects Receiving Booster Dose

Study Visit	V00	V01	V02	V03	V04	V05	V06	V07	V08	V09	V10	V11	V12	V13	V14	Unsch Visit	Early Term Visit
Study Day(s)	SCR -30 to -1	Day 1	Day 2 +1d	Day 4 +2d	Day 8 +2d	Day 29 ±3d	Day 57 ±3d	Day 113 ¹² -3d/+21d	Day 114 +1d	Day 116 +2d	Day 120 +2d	Day 142 ±3d	Day 170 ±3d	Day 293 ±3d	Day 478 ±7d		
Obtain Written Informed Consent	X																
Review Eligibility Criteria	X	X						X									
Medical History	X																
Review of Interim Medical History		X	X	X	X	X	X	X	X	X	X	X	X	X	X	X	X
Concomitant Medications	X	X	X	X	X	X	X	X	X	X	X	X	X	X	X	X	X
Vital Signs (Oral Temp, Pulse, BP)	X	X			X	X	X	X			X	X	X	X	X	X	X
Physical Examination Including Height and Weight	X																
Targeted Physical Examination, if Indicated		X			X	X	X	X			X	X	X	X	X	X	X
ECG ⁸		X ⁹			X	X	X	X ⁹			X	X	X	X	X		
Cardiac Biomarkers (Troponin T, CRP, ESR) ¹⁰		X ¹¹			X	X	X	X ¹¹			X	X	X	X			
Nasal Swab Collection for SARS-CoV-2 PCR	X															X ⁷	
Blood Collection for Safety Labs	X ¹				X ²		X ²				X ²		X ²	X ²		X ²	X ²
Blood Collection for HBsAg, Anti-HCV, SARS-CoV-2 Serology ³ , HIV	X						X ³						X ³				

Study Visit	V00	V01	V02	V03	V04	V05	V06	V07	V08	V09	V10	V11	V12	V13	V14	Unsch Visit	Early Term Visit
Study Day(s)	SCR -30 to -1	Day 1	Day 2 +1d	Day 4 +2d	Day 8 +2d	Day 29 ±3d	Day 57 ±3d	Day 113 ¹² -3d/+21d	Day 114 +1d	Day 116 +2d	Day 120 +2d	Day 142 ±3d	Day 170 ±3d	Day 293 ±3d	Day 478 ±7d		
Blood Collection for Cellular Immune Assays		X			X	X		X				X		X	X	X	X
Blood Collection for Antibody Assays		X				X	X	X				X		X	X	X	X
Vaccination		X						X									
45 Minute Evaluation After Study Vaccination		X						X									
Distribute Memory Aid and Study-Related Materials		X						X									
Review Memory Aid			X	X	X				X	X	X				X ⁴	X ⁴	
Adverse Events		X	X	X	X	X		X	X	X	X				X ⁵	X ⁵	
SAEs/AESIs Including PIMMCs/MAAEs/NOCMCs ¹³	X ¹⁴	X	X	X	X	X	X	X	X	X	X	X	X	X	X	X	X
Phone Visit ⁶			X	X					X	X							
Saliva Collection for Antibodies		X			X			X			X			X			

Abbreviations: AESI, adverse event of special interest; BP, blood pressure; d, day(s); ECG, electrocardiogram; HBsAg, hepatitis B surface antigen; HCV, hepatitis C virus; HIV, human immunodeficiency virus; MAAE, Medically Attended Adverse Event; NOCMC, New Onset Chronic Medical Condition; SAE, serious adverse event; PCR, polymerase chain reaction; PIMMC, Potentially Immune-Mediated Medical Condition; SARS-CoV-2, severe acute respiratory syndrome coronavirus 2; SCR, screening; Unsch, unscheduled

- Includes white blood cells (WBCs), hemoglobin (Hb), platelets (PLT), alanine aminotransferase (ALT), aspartate aminotransferase (AST), alkaline phosphatase (ALP), total bilirubin, creatine kinase (CK), serum creatinine, prothrombin time (PT)/international normalized ratio (INR), and activated partial thromboplastin time (aPTT)
- Includes WBC, Hb, PLT, ALT, AST, ALP, total bilirubin, CK, and creatinine
- Includes SARS-CoV-2 serology (N-specific) only
- If within 7 days after each vaccination (prime or boost dose)

- 5 If prior to Visit 11
- 6 Can be phone, text, or e-mail contact
- 7 A nasal swab for SARS-CoV-2 should be performed within 3 days of COVID-19 symptoms and repeated after 7 days.
- 8 ECG will be performed for subjects receiving booster dose in Cohorts 1 and 2. ECG data will include heart rate and RR, PR, QT, and QRS durations.
- 9 ECG will be performed before 1st and 2nd doses of vaccination.
- 10 Cardiac biomarker assessment will be performed for subjects receiving booster dose in Cohorts 1 and 2. Cardiac biomarker assessments will include troponin T, C-reactive protein (CRP), and erythrocyte sedimentation rate (ESR).
- 11 Cardiac biomarker assessment will be performed before 1st and 2nd doses of vaccination.
- 12 In case of second dose delay (allowed -3 days/+21 days), all safety visits (Visit 08 to Visit 12) will be scheduled based on the day of the second dose (e.g., Visit 08 will occur 1 day after delayed second dose and not on Day 114). All visits will shift based on the second dose without changing the time interval between 2 consecutive visits.
- 13 AESIs, including serologically or virologically confirmed SARS-CoV-2 infection and severity of COVID-19, PIMMCs, MAAEs, and NOCMCs will be collected from the time of first vaccination throughout the entire study.
- 14 SAEs occurring after signing of the informed consent form (ICF) will be recorded and reported to the sponsor or designee by the investigator within 24 hours of becoming aware of the SAE.

Table 3 Schedule of Assessments: Cohorts 3, 4, and 6

Study Visit	V00	V01	V02	V03	V04	V05	V06	V07	V08	V09	V10	V11	V12	V13	Unsch Visit	Early Term Visit
Study Day(s)	SCR -30 to -1	Day 1	Day 2 +1d	Day 4 +2d	Day 8 +2d	Day 15 ±2d	Day 29 ±3d	Day 30 +1d	Day 32 +2d	Day 37 +2d	Day 58 ±3d	Day 86 ±3d	Day 209 ±3d	Day 394 ¹⁶ ±7d		
Vaccination		X					X									
45 Minute Evaluation After Study Vaccination		X					X									
Distribute Memory Aid and Study-Related Materials		X					X									
Review Memory Aid			X	X	X			X	X	X					X ⁴	X ⁴
Adverse Events		X	X	X	X	X	X	X	X	X	X				X ⁵	X ⁵
SAEs/AESIs Including PIMMCs/MAAEs/NOCMCs ¹³	X ¹⁴	X	X	X	X	X	X	X	X	X	X	X	X	X	X	X
Phone Visit ⁶			X	X				X	X							
Saliva Collection for Antibodies		X			X	X	X			X			X			

Abbreviations: AESI, adverse event of special interest; BP, blood pressure; ECG, electrocardiogram; HBsAg, hepatitis B surface antigen; HCV, hepatitis C virus; HIV, human immunodeficiency virus; MAAE, Medically Attended Adverse Event; NOCMC, New Onset Chronic Medical Condition; SAE, serious adverse event; PCR, polymerase chain reaction; PIMMC, Potentially Immune-Mediated Medical Condition; SARS-CoV-2, severe acute respiratory syndrome coronavirus 2; SCR, screening; Unsch, unscheduled

1 Includes white blood cells (WBCs), hemoglobin (Hb), platelets (PLT), alanine aminotransferase (ALT), aspartate aminotransferase (AST), alkaline phosphatase (ALP), total bilirubin, creatine kinase (CK), serum creatinine, prothrombin time (PT)/international normalized ratio (INR), and activated partial thromboplastin time (aPTT)

2 Includes WBC, Hb, PLT, ALT, AST, ALP, total bilirubin, CK, and creatinine

3 Includes SARS-CoV-2 serology (N-specific) only

4 If within 7 days after each vaccination (prime or boost dose)

5 If prior to Visit 10

6 Can be phone, text, or e-mail contact

7 A nasal swab for SARS-CoV-2 should be performed within 3 days of COVID-19 symptoms and repeated after 7 days.

8 ECG data will include heart rate and RR, PR, QT, and QRS durations.

9 ECG will be performed up to 72 hours before the 1st and up to 72 hours before the 2nd study vaccinations.

10 Cardiac biomarker assessments will include troponin T, C-reactive protein (CRP), and erythrocyte sedimentation rate (ESR).

11 Cardiac biomarker assessment will be performed before 1st and 2nd doses of vaccination.

12 Cohort 6 only: women of childbearing potential must have a negative urine or serum pregnancy test at screening for eligibility purposes and within 24 hours prior to each study vaccination.

- 13 AESIs, including serologically or virologically confirmed SARS-CoV-2 infection and severity of COVID-19, PIMMCs, MAAEs, and NOCMCs will be collected from the time of first vaccination throughout the entire study.
- 14 SAEs occurring after signing of the informed consent form (ICF) will be recorded and reported to the sponsor or designee by the investigator within 24 hours of becoming aware of the SAE.
- 15 In case of second dose delay (± 3), all safety visits (Visit 07 to Visit 12) will be scheduled based on the day of the second dose (e.g., Visit 07 will occur 1 day after delayed second dose and not on Day 30). All visits will shift based on the second dose without changing the time interval between 2 consecutive visits.
- 16 Cohorts 3 and 4 will complete Visit 13 (Day 394) if the visit window occurs prior to the last study participant completing Visit 12 (Day 209). Cohort 6 will not complete Visit 13 (Day 394).

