Follow-up Duration	For Cohorts 1 and 2 (NOT receiving booster dose): 12 months For Cohorts 1 and 2 (receiving booster dose): 16 months For Cohorts 3 and 4: up to 13 months For Cohort 6: 7 months
Primary Objectives	
• To assess the safety and tolerability of 2 different doses (10 or 30 mcg) of GRT-R910 when administered to healthy adults (≥ 60 years of age) who were previously vaccinated with a first-generation Coronavirus Disease 2019 (COVID-19) vaccine (Cohorts 1 and 2; AstraZeneca)• To assess the safety and tolerability of a 10 mcg dose of GRT-R910 when administered to healthy adults (≥ 18 years of age) who were previously vaccinated with an mRNA-based COVID-19 vaccine (Pfizer/BioNTech, Moderna)

Primary Outcome Measures	
Occurrence of solicited local reactogenicity signs and symptoms for 7 days after GRT-R910 vaccinationOccurrence of solicited systemic reactogenicity signs and symptoms for 7 days after GRT-R910 vaccinationOccurrence of unsolicited adverse events (AEs) for 28 days after last study-administered GRT-R910 vaccinationChange from baseline for clinical safety laboratory parameters 7 days after last study-administered GRT-R910 vaccinationOccurrence of serious adverse events (SAEs) and adverse events of special interest (AESIs), including potentially immune-mediated medical conditions (PIMMCs), medically attended adverse events (MAAEs), and new onset chronic medical conditions (NOCMCs), throughout the entire study after GRT-R910 vaccination
Secondary Objective	
To assess the cellular and humoral immunogenicity of GRT-R910 when administered to volunteers (≥ 60 years of age for Cohorts 1, 2, 3, and 4 and ≥ 18 to ≤ 59 years of age for Cohort 6) who were previously vaccinated with either an adenoviral COVID-19 vaccine (AstraZeneca, Janssen) or an mRNA-based COVID-19 vaccine (Pfizer/BioNTech, Moderna)
Secondary Outcome Measures	
Response rate, and magnitude of SARS-CoV-2-specific antibody binding and neutralization in serum samplesResponse rate, magnitude, and breadth of SARS-CoV-2 specific T-cells as assessed by interferon (IFN)-γ enzyme-linked immunospot (ELISpot) in 10 subjects per cohort
	[REDACTED]

Rationale

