12.2 Sample Size Considerations

The targeted sample size for each of the study cohorts was determined based on previous Phase 1 studies. Recruitment for GRT-R910 boost vaccination schedules will target enrolling 50 volunteers as follows:

- Cohort 1 (N=10, including 2 sentinels): 10 mcg GRT-R910 (after AstraZeneca) 2 doses, homologous prime-boost, booster dose will be 113 days (16 weeks) after the prime for adults ≥ 60 years of age.
- Cohort 2 (N=10, including 2 sentinels): 30 mcg GRT-R910 (after AstraZeneca) 2 doses, homologous prime-boost, booster dose will be 113 days (16 weeks) after the prime for adults ≥ 60 years of age.
- Cohort 3 (N=10): 10 mcg GRT-R910 (dose selected from Cohorts 1 and 2) after adenovirus-based vector vaccine, homologous prime-boost, booster dose will be 28 days after the prime for adults ≥ 60 years of age.
- Cohort 4 (N=10): 10 mcg GRT-R910 (dose selected from Cohorts 1 and 2) after mRNA vaccine, homologous prime-boost, booster dose will be 28 days after the prime for adults ≥ 60 years of age.
- Cohort 6 (N=10): 10 mcg GRT-R910 (dose selected from Cohorts 1 and 2) after mRNA vaccine, homologous prime-boost, booster dose will be 28 days after the prime for adults ≥ 18 to ≤ 59 years of age.

Sample size and power analysis for safety

The goal of the safety evaluation for this study is to identify safety concerns associated with product administration. The ability of the study to detect SAEs (see [Section 11.1.2](#)) can be expressed by the true event rate above which at least 1 SAE would likely be observed.

For each group of 10 subjects, there is an 89% chance of observing at least 1 event if the true rate is 20% or higher.

Binomial probabilities of observing at least 1 event among groups of size 10, 20, or 30 overall are presented in [Table 5](#) for a range of possible true adverse event rates. These calculations provide a more complete picture of the sensitivity of the study design to identify potential safety problems with the vaccine.

Table 5 Probability (%) of Detecting at Least 1 Adverse Event Under Different Incidence Rates

Incidence Rate (%)	Sample Size = 10	Sample Size = 20	Sample Size = 30
0.01	0.10	0.20	0.30
0.1	1.00	1.98	2.96
1.0	9.56	18.21	26.03
2.0	18.29	33.24	45.45
5.0	40.13	64.15	78.54
10.0	65.13	87.84	95.76
20.0	89.26	98.85	99.88

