12.3 Treatment Assignment Procedures

12.3.1 Assignment Procedures

Cohorts 1 and 2 will be enrolled sequentially following dose-escalation rules. Two sentinels in each cohort will be observed for 72 hours for safety in each dose cohort. If no halting rules are met after the 2 sentinels in each cohort have been observed for 72 hours after study vaccination, the remaining 8 volunteers will be enrolled in each cohort.

The dose for Cohorts 3, 4, and 6 was selected from Cohorts 1 and 2 after evaluation of reactogenicity, safety, and initial immunogenicity. Dose selection will be determined by the Gritstone clinical team in consultation with the PI(s). Cohorts 3, 4, and 6 will be enrolled in parallel. There will be no sentinel dosing in Cohorts 3, 4, and 6.

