12.4.3 Analysis of the Secondary Endpoint(s)

Antibody titers (binding and neutralizing antibody) will be described by group and timepoint using geometric mean titer (GMT) and geometric fold-rise (GMFR), including 95% confidence intervals based on the t-distribution. Undetectable titers will be imputed as one-half of the lower limit of quantitation and the number and proportion of subjects with undetectable titers at each timepoint will be reported. Response will be defined as a 4-fold increase in antibody titer over baseline. Definitions of response as a 2-fold or 8-fold rise may also be explored. The number and percent of subjects achieving seroconversion by group and timepoint will be summarized,

including 95% exact confidence intervals. Plots such as reverse cumulative distributions or longitudinal presentations of GMTs will be presented.

Analysis of ICS endpoints will present the percent of cells expressing various cytokines or combinations of cytokines, including 95% confidence intervals, tabularly and graphically by group, peptide pool/stimulant, and time point. ELISpot results will be summarized by cytokine, group, peptide pool/stimulant, and time point using summary statistics and 95% confidence intervals.

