- 13 AESIs, including serologically or virologically confirmed SARS-CoV-2 infection and severity of COVID-19, PIMMCs, MAAEs, and NOCMCs will be collected from the time of first vaccination throughout the entire study.
- 14 SAEs occurring after signing of the informed consent form (ICF) will be recorded and reported to the sponsor or designee by the investigator within 24 hours of becoming aware of the SAE.

Gritstone bio, Inc.
GO-009

Statistical Analysis Plan, Version 5.0
Date Issued: 09JUN2023

Table 8 Schedule of Study Procedures: Cohorts 3, 4, and 6

Study Visit	V00	V01	V02	V03	V04	V05	V06	V07	V08	V09	V10	V11	V12	V13	Unsch Visit	Early Term Visit
Study Day(s)	SCR -30 to -1	Day 1	Day 2 +1d	Day 4 +2d	Day 8 +2d	Day 15 ±2d	Day 29 ±3d	Day 30 +1d	Day 32 +2d	Day 37 +2d	Day 58 ±3d	Day 86 ±3d	Day 209 ±3d	Day 394 ¹⁶ ±7d		
Obtain Written Informed Consent	X															
Review Eligibility Criteria	X	X						X								
Medical History	X															
Review of Interim Medical History		X	X	X	X	X	X	X	X	X	X	X	X	X	X	X
Concomitant Medications	X	X	X	X	X	X	X	X	X	X	X	X	X	X	X	X
Vital Signs (Oral Temp, Pulse, BP)	X	X			X	X	X			X	X	X	X	X	X	X
Physical Examination Including Height and Weight	X															
Targeted Physical Examination, if Indicated		X			X		X			X	X	X	X	X	X	X
ECG ⁸		X ⁹			X		X ⁹			X	X	X	X	X		
Cardiac Biomarkers (Troponin T, CRP, ESR) ¹⁰		X ¹¹			X		X ¹¹			X	X	X	X	X		
Nasal Swab Collection for SARS-CoV-2 PCR	X														X ⁷	
Blood Collection for Safety Labs	X ¹				X ²		X			X ²		X ²	X ²		X ²	X ²
Blood Collection for HBsAg, Anti-HCV, SARS-CoV-2 Serology ³ , HIV	X												X ³			
Blood Collection for Cellular Immune Assays		X			X		X			X		X	X	X		
Blood Collection for Antibody Assays		X				X	X			X	X	X	X	X	X	X
Pregnancy Test (Women of Childbearing Potential)	X ¹²	X ¹²					X ¹²									

Study Visit	V00	V01	V02	V03	V04	V05	V06	V07	V08	V09	V10	V11	V12	V13	Unsch Visit	Early Term Visit
Study Day(s)	SCR -30 to -1	Day 1	Day 2 +1d	Day 4 +2d	Day 8 +2d	Day 15 ±2d	Day 29 ±3d	Day 30 +1d	Day 32 +2d	Day 37 +2d	Day 58 ±3d	Day 86 ±3d	Day 209 ±3d	Day 394 ¹⁶ ±7d		
Vaccination		X					X									
45 Minute Evaluation After Study Vaccination		X					X									
Distribute Memory Aid and Study-Related Materials		X					X									
Review Memory Aid			X	X	X			X	X	X					X ⁴	X ⁴
Adverse Events		X	X	X	X	X	X	X	X	X	X				X ⁵	X ⁵
SAEs/AESIs Including PIMMCs/MAAEs/NOCMCs ¹³	X ¹⁴	X	X	X	X	X	X	X	X	X	X	X	X	X	X	X
Phone Visit ⁶			X	X				X	X							
Saliva Collection for Antibodies		X			X	X	X			X			X			

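### If only part of Cohort 3 or 4 reaches Day 394, by-timepoint titer summaries mix change in titer with change in who is sampled; a paired Day 209 to Day 394 summary would separate them at no cost

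*Protocol*

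**What the plan says.** Footnote 16 to the schedule for Cohorts 3, 4 and 6 (Protocol 3.2, Table 3; repeated in SAP Appendix 1, Table 8) states: "Cohorts 3 and 4 will complete Visit 13 (Day 394) if the visit window occurs prior to the last study participant completing Visit 12". Cohort 6 has no Day 394 visit. The synopsis gives the resulting variable follow-up: "For Cohorts 3 and 4: up to 13 months". Protocol 12.3.1 adds: "Cohorts 3, 4, and 6 will be enrolled in parallel". The last participant may therefore belong to any of the three cohorts, each planned at 10 subjects.

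In SAP Table 8 the row "Blood Collection for Antibody Assays" is marked at both V12 (Day 209) and V13 (Day 394), and so is the row for cellular assays.

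On analysis, Protocol 12.4.3 says: "Antibody titers (binding and neutralizing antibody) will be described by group and timepoint using geometric mean titer (GMT) and geometric fold-rise (GMFR", with t-based 95% intervals. It continues: "Plots such as reverse cumulative distributions or longitudinal presentations of GMTs will be presented". Under Protocol 12.4.1 the default summaries use subjects with non-missing values. The immunogenicity population in Protocol 12.4 needs only some post-dose data, not data at both late visits. SAP Sections 1 and 8.2 leave immunogenicity to a separate SAP, which was not among the documents.

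**The concern.** Footnote 16 lets enrolment date decide who has a Day 394 sample. Any loss between Day 209 and Day 394 is then partly planned truncation rather than ordinary dropout. A by-timepoint GMT at Day 209 could rest on up to 10 subjects in a cohort, and the one at Day 394 on the earlier-enrolled part of the same cohort. A line joining the two GMTs would show change in titer plus change in composition.

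GMFR does not remove this. It pairs each visit with baseline, but the Day 209 and Day 394 fold-rises could still rest on different sets of subjects.

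At stake is how persistence is read for the 28-day schedule. Day 394 is its only point one year after the booster (394 − 29 = 365 days). Boosted subjects in Cohorts 1 and 2 have a matching point without the calendar condition (478 − 113 = 365 days), so a reader may set a whole-cohort curve beside a truncated one. Subjects can also differ by calendar time. Protocol 7.1 allows earlier booster doses and sets a minimum but no maximum time since the last vaccine.

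**Working it through.** **1. The plan's own figures.** The documents give no figure for titers at these visits. Their only computed figures, the detection probabilities in Protocol Table 5, reproduce in all 21 cells (for example 1 − 0.8^10 = 0.8926), but they concern adverse events.

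**2. Who reaches Day 394.** Inputs from Table 3: V12 is Day 209 ± 3 and V13 is Day 394 ± 7. The required lead over the last participant is the V13 day minus the V12 day:
- shortest: 387 − 212 = 175 days
- nominal: 394 − 209 = 185 days
- longest: 401 − 206 = 195 days

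**3. How many that could be.** Enrolment dates are not given, so these are illustrations with 10 evenly spaced subjects per cohort.

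| Cohort 3 or 4 enrols over | Last participant enrols on day | Number reaching Day 394 |
|---|---|---|
| 150 days | 150 | 0 |
| 240 days | 240 | 2–3 |
| 300 days | 300 | 4 |
| 365 days | 365 | 5 |
| 90 days | 240 | 5–7 |
| 90 days | 280 | 9–10 |

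Composition matters only when a cohort is partly retained.

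**4. Chance composition, no true change in anyone.** Let s be the between-subject SD of log10 titer and k the number of 10 who reach Day 394 (both assumed). The SD of (subset mean − full-cohort mean) is s × √(1/k − 1/10).
- s = 0.3, k = 5: 0.095, or 1.24-fold
- s = 0.5, k = 4: 0.194, or 1.56-fold; 95% range 10^(1.96 × 0.194) = 2.4-fold either way
- s = 0.6, k = 3: 0.290, or 1.95-fold

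**5. Systematic composition.** If early enrollees have titers r times those of late enrollees, the GMT ratio with no true change is r^(1 − k/10). For an assumed r = 2 it is 1.62 (k = 3), 1.41 (k = 5) or 1.15 (k = 8), a false rise. With r = 1/2 the same factors appear as false waning. The documents give neither the size nor the direction of r.

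**6. What pairing does.** 50,000 cohorts were simulated with no true change, between-subject SD 0.5, within-subject SD 0.1 at each visit, r = 2 and k = 5. The available-case ratio was wrong by more than 1.5-fold in 46.5% of cohorts, and the paired ratio in 0.5%. The paired ratio had median 1.00 and 95% range 0.75 to 1.33. The SD of 0.1 allows for no difference between subjects in rate of waning, so it favours pairing.

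**The case against.** The strongest reply is that a descriptive Phase 1 study plans no inference about this interval. Protocol 12.1 rules out hypothesis testing between schedules and cohorts. The secondary outcomes are response rate, magnitude and T-cell breadth, and no decay rate or durability endpoint is defined. This stands, and it limits the point to presentation.

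Second, the plan already shows its uncertainty. Under the assumptions in step 4, the t-based interval on the Day 394 GMT has these half-widths:
- s = 0.5, k = 4: 3.182 × 0.5/√4 = 0.796, or 6.2-fold
- s = 0.3, k = 5: 2.776 × 0.3/√5 = 0.372, or 2.4-fold
- s = 0.6, k = 3: 4.303 × 0.6/√3 = 1.491, or about 31-fold

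Each is far wider than the chance effect, so a careful reader would claim little. That also stands, but these intervals describe the level at one visit, not the change between two. With the within-subject SD of 0.1 at each visit, the paired half-width at k = 4 is 3.182 × 0.1 × √2/√4 = 0.225, or 1.7-fold, and it measures the change itself.

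Third, much is already in hand: the number with data is a default statistic, follow-up is disclosed as variable, and subject listings would let a reader rebuild the pairs.

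A reader might infer three stronger things that the documents do not support:
- *The two visits compare different people.* Apart from missed visits, those seen at Day 394 are a nested subset of those seen at Day 209.
- *Only the earliest enrollees will be seen.* That depends on enrolment dates not given; step 3 runs from 0 to all 10.
- *No paired analysis is planned.* Protocol 12.4.3 is an outline with an open list of plots, and the separate immunogenicity SAP may already pair.

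**Conclusion.** The point holds in conditional form. If part, but not all, of Cohort 3 or 4 reaches Day 394, the by-timepoint GMTs and GMFRs and any longitudinal plot mix true change with change in composition. The supplied documents state no rule that separates the two.

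The chance part is about 1.2- to 2-fold (one SD) for assumed log10 SDs of 0.3 to 0.6 and 3 to 5 of 10 subjects. It is sampling variation rather than bias. Bias would need early and late enrollees to differ, which is plausible but has no documented size or direction. If none or all of a cohort reaches Day 394, footnote 16 creates no composition effect.

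The plan is not wrong as written, and no dose choice or decision rule depends on this comparison. A paired summary is simply the better method for the interval and uses samples already planned.

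**What to change.** In Protocol 12.4.3 and the immunogenicity SAP, for Cohorts 3 and 4:

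1. Report the within-subject geometric mean ratio of titer, V13/V12, with a t-based 95% CI, in subjects with both samples. With fewer than two such subjects, list the values only.
2. Draw the V12-to-V13 segment of longitudinal GMT plots, and give the matching ELISpot summaries, in those same subjects.
3. Label V13 as the early-enrolled subset and print its n. State that pairing removes the composition artefact but does not make the subset representative of the cohort.

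The cost is one extra table row, one plotting rule and a footnote, with no new visits, samples or subjects. If every subject has both samples, the paired ratio equals the ratio of the two GMTs, so nothing is lost. The rule is best fixed before late titers are seen, so that the choice of curve cannot depend on which looks more durable. If the immunogenicity SAP already pairs these visits, only the label and a cross-reference in Protocol 12.4.3 are needed.
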